### **3. Statistical Power, Aim 2**

Primary outcomes: Data from a previous study in the *ECS* population identified that 31% of infants had  $\text{BMI} \geq 85^{\text{th}}$  percentile at age 9 months. Assuming this represents the *ECS* control population for this pilot study, 15 infants per group would provide 42% power to detect the reduction of this rate to 0% by 9 months in the intervention group, at  $p < 0.05$ . A similar power (43%) was obtained when modeling continuous change in  $\text{BMI}$  percentile between 3 and 9 months of age, which had a mean (SD) change of 19.6 (29.3) percentile points, assuming the intervention group would achieve no mean change in  $\text{BMI}$  percentile and equal variance with the control group. Thus, this study will be underpowered to identify significant changes due to the intervention, but will enable estimation of the effect size to power larger studies.

Secondary outcomes: Previous observational data from a cohort of Cincinnati infants living in an urban environment found that the number of food groups fed increased by an average of  $3.4 \pm 1.4$  food groups between ages 3-9 months. (Woo 2015) Assuming equal variance between the intervention and control groups, and 15 infants per group, this pilot study would have 75% power to detect a 1 SD (1.4 food group) difference in the increase of food groups between intervention groups at  $p < 0.05$ . We thus anticipate that this pilot intervention will also be underpowered to evaluate changes in our secondary outcomes of infant diet, but will be informative with regard to the anticipated effect size and resulting sample size required in a larger trial.

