| | 
We do not anticipate difficulty with reaching adequate study enrollment given the number of eligible participants significantly exceeds the number of participants required for this pilot trial (i.e., approximately 400 families will enroll in ECS during the 6-month recruitment period and only 30 families are required for study enrollment). Our team has a successful track record of enrollment of ECS families into supplemental intervention trials. However, it is possible we may encounter participant attrition. We will take several safe guards to reduce attrition. All intervention and study visits will be conducted in participants' homes to reduce barriers to attendance. Multiple methods for contacting families will also be obtained, including contact information for friends and family members who are likely to know the location of participants should they be temporarily out of contact. Regarding the GLA phase, GLA and action planning sessions will be scheduled at times likely to be convenient to participants, such as evenings and weekends, and if we encounter recruitment challenges, we could conduct multiple GLA sessions to meet participant availability.
 |
| | 
3.2 Describe the time that you will devote to conducting and completing the research, i.e. percent effort.
 
PI will have 15% effort on this project.
 |
| | 
3.3 Describe the availability of medical or psychological resources that subjects might need as a result of an anticipated consequences of the human research.
 |
| | 
The intervention tested in this study (HEMI) is trauma-informed and includes trauma-specific treatment components if participants have a significant trauma history. This is because stress and trauma can have a significant impact on feeding and eating, and we know rates of trauma are high in our target enrollment population. The research study
 |

TEMPLATE: RESEARCH PROTOCOL

| NUMBER | ACTIVE DATE | PAGE |
|---------|-------------|---------|
| HRP-503 | 02-04-2020 | 9 of 44 |

interventionists are graduate students in Clinical Psychology and trained in discussion and treatment of trauma. However, families may feel uncomfortable talking about these topics, and our research study can provide psychological referral resources if families would like that information.

3.4 Describe your process to ensure that all persons assisting with the research are adequately informed about the protocol, the research procedures, and their duties and functions.

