| 
16.0 POTENTIAL BENEFITS TO SUBJECTS
 | 
16.1 Describe the potential benefits that individual subjects may experience from taking part in the research. It may be useful to include: the probability, magnitude, and duration of the potential benefits. Indicate if there is no direct benefit to subjects. Do not include benefits to society or to others.
 
Mothers may benefit from participation in the study through receipt of a potentially efficacious intervention to promote healthy infant feeding and reduce subsequent obesity-risk.
 |
| 
17.0 DATA MANAGEMENT AND CONFIDENTIALITY
 | 
17.1 Describe the data analysis plan, including any statistical procedures or power analyses.
 
Aim 1: GLA data analysis will be conducted in real-time by the participants during the session. Participants will reach consensus on overall themes and action items.
 
Aim 2: Proportion of infants with BMI ≥ 85th percentile will be compared between the treatment and control group using a Fisher's exact test of independence, including all randomized participants in an intention to treat framework. If baseline differences are found between groups, these baseline variables will be included in an adjusted logistic regression model with odds ratios of the intervention group estimated relative to the control group. Sensitivity analyses will examine the impact of treatment fidelity on intervention efficacy. Secondary outcomes of infant diet diversity and servings of fruits and vegetables will be evaluated using general linear models, adjusting for baseline characteristics as needed. Infant biological sex and participation in other supplemental nutrition programs (e.g., WIC) will be explored as potential moderators of treatment outcomes.
 
17.2 Describe the steps that will be taken to secure the data.
 |

TEMPLATE: RESEARCH PROTOCOL

| NUMBER | ACTIVE DATE | PAGE |
|---------|-------------|----------|
| HRP-503 | 02-04-2020 | 21 of 44 |

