### **2. Analyses**

For Aim 1, GLA data analysis will be conducted in real-time by the participants during the session. Facilitated by Co-I [name], participants will reach consensus on overall themes and action items, such as the content to be included in each treatment module. Demographic information of stakeholders will be summarized using descriptive statistics.

**For Aim 2**, descriptive statistics of the study population will be summarized. Treatment adherence will be assessed as the number of treatment visits completed within 1 week of the monthly time window. Missed visits will trigger an analysis of the situation and attempted communication with the mother to gather additional information about why study visits were not completed. Treatment fidelity will be assessed using coding of audiotapes for 25% of the visits. The maternal feedback on the program will be conducted at the post-treatment visit, and qualitative/open ended questions will be coded and analyzed for themes for improvement of the intervention. Peer counselor feedback on the program will be assessed through interviews after all treatment sessions have been delivered. Responses to open-ended questions will be analyzed for themes and also used to further modify the intervention.

For all Aim 2 effectiveness outcome variables, analyses will be conducted using two-sample t-tests or non-parametric Wilcoxon rank sum tests to evaluate between-group differences for continuous variables, and Fisher's exact tests of contingency tables for categorical variables. Prior to conducting analyses, distributions of outcome variables will be assessed to determine the appropriate modeling approaches. All primary analyses will be conducted using intention to treat (ITT) analysis, including all individuals who were enrolled. Given the small sample size, imbalances may arise between the randomized study groups. If groups are unbalanced at baseline, these baseline variables will be included in adjusted general linear model or logistic regression models, depending on the outcome, with adjusted differences in outcomes estimated by intervention group. P-values  $< 0.05$  will be considered significant. Every attempt will be made to collect demographic and psychosocial covariate measures. However in the event of missing covariate data, we will use multiple imputation techniques to handle missing data in the statistical models.

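### The 42% power stated for the binary primary outcome is not the power of the planned Fisher's exact test, which is 51.9% two-sided on the SAP's own inputs; the method behind 42% is not given

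*SAP*

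**What the plan says.** SAP section 3 takes its control rate from earlier data: "Data from a previous study in the *ECS* population identified that 31% of infants had" a BMI at or above the 85th percentile at 9 months. For a significance level of 0.05, it then states that "15 infants per group would provide 42% power to detect the reduction of this rate to 0% by 9 months in the intervention group". No test, sidedness, approximation or software is named for this figure.

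The same section gives two other powers at 15 per group. For the continuous version of the primary outcome, "A similar power (43%) was obtained when modeling continuous change in" BMI percentile, with a mean change of 19.6 (SD 29.3) in controls against no mean change. For diet diversity it claims "75% power to detect a 1 SD (1.4 food group) difference in the increase of food groups".

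The test for the binary outcome is named twice. SAP section 2 lists "Fisher's exact tests of contingency tables for categorical variables", and Protocol 17.1 compares the proportions "using a Fisher's exact test of independence". Neither document says whether the test is one- or two-sided; the outcome table in SAP section 1 gives only a directional hypothesis.

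The SAP concludes that the trial will be underpowered and is meant to supply an effect size for a larger study. On retention, Protocol 3.1 says "it is possible we may encounter participant attrition" and lists safeguards against it.

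**The concern.** A stated power should be the power of the test the plan specifies, at the inputs given beside it. Here the inputs are complete (31% v 0%, 15 per group, 0.05) and the test is named in both documents, so the figure can be checked exactly. It does not reproduce.

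Two things are at stake, both modest. Someone planning the larger study from this section cannot reproduce the calculation without guessing its method. The section also presents the binary and continuous versions of the primary outcome as having nearly the same power, whereas under the planned tests they are about 52% and 42%.

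**Working it through.** **Inputs.** Control rate 0.31, intervention rate 0, 15 per group and alpha 0.05 (SAP section 3). Fisher's exact test (SAP section 2, Protocol 17.1). 1:1 allocation (Protocol 6.2).

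**Step 1: sidedness, from the SAP's other two figures.** Two-sample t-test, 28 degrees of freedom, non-centrality = (difference/SD) × √(15/2).

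| Outcome | Non-centrality | Two-sided power | One-sided power | SAP states |
|---|---|---|---|---|
| Change in BMI percentile, 19.6/29.3 | 1.832 | 42.4% | 55.7% | 43% |
| Food groups, 1.4/1.4 | 2.739 | 75.3% | 84.8% | 75% |

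Both fit a two-sided test at 0.05, and neither fits a one-sided one. Two-sided is therefore the consistent reading of the section.

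**Step 2: rejection rule for Fisher's test.** At a true rate of 0% the intervention arm always shows 0/15, so only the control count x matters. The one-sided p-value is C(15, x)/C(30, x). With equal arms the two-sided value is twice that.

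- x = 4: 1365/27405 = 0.0498, two-sided 0.0996. Not significant.
- x = 5: 3003/142506 = 0.0211, two-sided 0.0421. Significant.

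**Step 3: power.** P(X ≥ 5) for X ~ Binomial(15, 0.31):

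1 − (0.0038 + 0.0258 + 0.0811 + 0.1579 + 0.2128) = 1 − 0.4813 = **0.5187**

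Summation over all 16 × 16 tables gives the same value. Rounding of 31% does not close the gap: 30.5% gives 50.2% and 31.5% gives 53.6%. One-sided Fisher at 0.05 rejects from x = 4 and has power 73.1%, further from 42%.

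**Step 4: where 42% might come from.** Several routes land near it, and the documents point to none.

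- Normal approximation with a shortcut continuity correction, effective n = 15 − 2/0.31 = 8.55: 41.7%. The full continuity correction gives 44.8%.
- Two-sided t-test on 0/1 data with the control-arm SD √(0.31 × 0.69) in both arms: 42.6%.
- Two-sided Fisher with an intervention rate of 2%: 41.8%, but the SAP states 0%.

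**Step 5: how firm is 52%?** The documents give no post-randomisation retention rate (the 85% in Protocol 11.2 is retention in the home visiting programme before enrolment) and no intervention rate other than 0%. The rows below the first are therefore assumptions.

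| Measured per group | Intervention rate | Two-sided Fisher power |
|---|---|---|
| 15 | 0% | 51.9% |
| 14 | 0% | 44.9% |
| 13 | 0% | 37.6% |
| 12 | 0% | 30.3% |
| 15 | 1% | 46.6% |
| 15 | 2% | 41.8% |
| 14 | 1% | 40.3% |
| 12 | 2% | 24.7% |

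For 12 to 15 per group with no intervention events, the rule stays at 5 control events (4 v 0 gives p between 0.093 and 0.100), so equal losses lower power steadily. Unequal losses behave irregularly because the test is discrete. With 14 controls and 15 intervention infants, 4 v 0 gives p = 0.042 and power is 67.5%. With 15 controls and 14 intervention infants it remains 51.9%.

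**The case against.** The SAP never says that 42% is a Fisher power. At least two approximations give about 42% at the stated inputs, so what is shown is an undisclosed method, not a proven slip in arithmetic. **This stands as to cause:** the documents do not settle where 42% came from. It does not remove the mismatch, because 42% is not the power of the planned test and the reader is not told what it is the power of.

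Two-sidedness is inferred. **True**, but the SAP's other figures support it, and the one-sided value misses 42% by more.

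Fisher's test may not be the final analysis, since both documents move to adjusted logistic regression if baseline imbalance appears. **True, and 52% does not apply to that model.** But the adjusted analysis is conditional, and Fisher's test is the one specified for the unadjusted comparison.

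The effect is slight: the SAP already calls the study underpowered, the stated figure is the lower one, and plausible attrition with a small non-zero rate brings the exact power back to about 42% or below. **This stands and limits the weight of the point.** It is also the reason for not replacing 42% with a bare 52%.

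**Conclusion.** The point holds. Two-sided Fisher power for 31% v 0% with 15 per group is 51.9% (50.2% to 53.6% over the rounding of 31%), 9.9 percentage points above the stated 42%. This rests on a two-sided 0.05 level, exactly zero events in the intervention group, and all 30 infants measured at 9 months. The origin of 42% cannot be established from the documents.

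The practical weight is low. On the SAP's own assumptions the stated figure errs on the cautious side, the conclusion that the trial is underpowered is unchanged, and nothing follows for sample size or analysis. It should be corrected because it describes a primary outcome and cannot be reproduced as written.

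**What to change.** Replace the sentence in SAP section 3 with wording such as:

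> With 15 infants per group, all measured at 9 months, power is 52% for 31% v 0% (two-sided Fisher's exact test, alpha 0.05). As assumptions, this falls to 45%, 38% or 30% if 14, 13 or 12 in each group are measured, and to 47% or 42% if the intervention rate is 1% or 2%.

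If 42% was meant to rest on another method or a non-zero intervention rate, keep it and name that method or rate beside it. The following comparison with 43% should then be reworded, since at 52% the two powers are no longer similar.

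A separate, optional addition to SAP section 2 would suit the aim of estimating an effect size: report between-group differences with 95% confidence intervals. At 15 per group the expected half-width, 2.048 × SD × √(2/15), is about 22 BMI percentile points (SD 29.3) and about 1 food group (SD 1.4).

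The cost is SAP wording only, with no change to sample size, data collection or the planned tests.

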| | 
For Aim 1, there will be no more than 100 participants.
 
For Aim 2, we will recruit 30 infants and their mothers.
 
11.2 If applicable, distinguish between the number of subjects who are expected to be enrolled and screened, and the number of subjects needed to complete the research procedures.
 
Approximately 15 women enroll in the ECS program each week (~800 per year), providing a large sample pool from which to enroll participants. We anticipate that 50% (n=400) of eligible ECS mother-child dyads will be referred to the study (~7-8 per week). Participants will receive their enrollment visit when the child is 2-months of age. Informed by retention data from the ECS program, 85% (n=340) of the participants will remain active in the program when child is 2-months of age (criterion for eligibility). We anticipate 60% will agree to participate in the study (~4 per week).
 |
| 
12.0 RECRUITMENT METHODS
 | 
12.1 Describe when, where, and how potential subjects will be recruited.
 
GLA Phase: Leadership, board members, community partners, and home visitors will be invited for involvement in the GLA through personal correspondence and advertising through standard ECS communications and meetings. Participating families will be informed about the study by ECS home visitors. Word-of-mouth and snowballing (i.e., one participant informing others who might be interested in the
 |

TEMPLATE: RESEARCH PROTOCOL

| NUMBER | ACTIVE DATE | PAGE |
|---------|-------------|----------|
| HRP-503 | 02-04-2020 | 18 of 44 |

assessment) will also be largely utilized. Prior to the start of the GLA session, participants will be provided with the required elements of consent.

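### The 75% and 43% powers in SAP 3 hold only if all 15 infants per arm have a 9-month outcome; they should be labelled as no-loss values, and the binary 42% recomputed with the planned Fisher test

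*SAP*

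**What the plan says.** SAP section 3 (Statistical Power, Aim 2) gives three powers.

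- **Binary BMI outcome**, 31% in controls against 0%: "15 infants per group would provide 42% power to detect the reduction of this rate to 0% by 9 months in the intervention group".
- **Change in BMI percentile**, mean 19.6 (SD 29.3) against no change: 43%. The sample size is not repeated, but the context is the same 15 per group.
- **Diet diversity**, where the arms differ by one SD, or 1.4 food groups: "Assuming equal variance between the intervention and control groups, and 15 infants per group, this pilot study would have 75% power".

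The same section says that the study is underpowered for the BMI outcomes and for diet, and that its use is to estimate effect sizes for a larger trial.

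On numbers, protocol 11.1 says: "For Aim 2, we will recruit 30 infants and their mothers". Allocation is 1:1, so this is 15 per arm with no margin. Outcomes are measured at 2 and 9 months of age (protocol 6.2). Protocol 3.1 says: "However, it is possible we may encounter participant attrition". It then lists safeguards, such as home visits and several contact routes. Protocol 11.2 describes referral, continued programme activity and agreement to take part, but gives no number expected to complete.

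SAP section 2 plans an intention-to-treat analysis of everyone enrolled, using t or Wilcoxon tests for continuous outcomes and Fisher's exact test for categorical ones. Multiple imputation is planned for missing covariates. Nothing is said about a missing outcome.

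**The concern.** The number recruited and the number analysed in the power calculation are the same, 15 per arm. That requires complete outcome data after seven months of follow-up, and the SAP does not say that it assumes this. The intention-to-treat wording does not close the gap. The planned two-sample tests need an observed 9-month value, and without a rule for missing outcomes a lost infant leaves the comparison.

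The stake is the accuracy of the stated figures. A reader who plans the larger trial from this pilot needs to know that the 75% and 43% are upper values. The number of infants expected to reach the 9-month measurement is also something that a pilot should state.

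**Working it through.** **Inputs.** From SAP 3: 15 per group; diet difference 1 SD, so d = 1.0; BMI-percentile change d = 19.6/29.3 = 0.669; binary rates 31% and 0%. From SAP 2: significance level 0.05 and the tests. From the protocol: 30 recruited, 1:1. Assumed here: two-sided tests (the SAP does not give the sidedness, but two-sided reproduces the 75%) and 14, 13 or 12 evaluable infants per arm, a loss of 1/15 = 7% to 3/15 = 20%. The documents give no figure for this loss.

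**Continuous outcomes.** Two-sample t-test with n per arm, 2n − 2 degrees of freedom and noncentrality d × √(n/2). Power is the probability that the noncentral t exceeds the two-sided critical value in absolute size.

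The plan's own figures first, at n = 15 (28 degrees of freedom, critical value 2.048):

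- Diet: noncentrality 1.0 × √7.5 = 2.739; power 75.3%. The SAP says 75%, so it reproduces.
- BMI change: noncentrality 0.669 × √7.5 = 1.832; power 42.4%. The SAP says 43%, so it reproduces to within one point.

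**Binary outcome.** Exact two-sided Fisher power. With a true rate of 0% the intervention arm has no events, so power is the probability that the control arm has enough events for p < 0.05. At 15 per arm, 4 against 0 gives p = 0.0996 and 5 against 0 gives p = 0.042, so 5 are needed. P(X ≥ 5) for X ~ Binomial(15, 0.31) is 51.9%. The SAP says 42%, so this one does not reproduce with the planned test. Two other calculations come close to 42%: a t-type calculation with the control-arm SD, √(0.31 × 0.69), gives 42.6%, and Fisher with about 2% in the intervention arm gives 41.8%. The documents do not say which method was used.

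**With loss.** Five control events are still needed at 14, 13 and 12 per arm.

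| Evaluable per arm | Diet, d = 1.0 | BMI change, d = 0.669 | Binary BMI, Fisher, 31% v 0% |
|---|---|---|---|
| 15 (no loss) | 75.3% | 42.4% | 51.9% |
| 14 | 72.1% | 39.9% | 44.9% |
| 13 | 68.7% | 37.4% | 37.6% |
| 12 | 64.9% | 34.7% | 30.3% |

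The binary outcome loses most, because the number of control events needed stays at five while the number of control infants falls.

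**Precision.** The half-width of the 95% interval for a mean difference, in SD units, is the critical t × √(2/n). This is 0.75 at 15 per arm, 0.81 at 13 and 0.85 at 12.

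**The case against.** The strongest reply is that the SAP already draws the right conclusion. It calls the study underpowered for BMI and, directly after the 75%, for diet as well. A fall from 75% to between 72% and 65% leaves that judgement where it was. This stands, and it limits the point to correcting stated numbers. A reader might infer that the SAP presents the diet outcome as adequately powered; its next sentence says the opposite.

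The second reply is that the documents do not forecast any particular loss. This also stands. The protocol calls attrition possible and lists safeguards. Its background links poor attrition to programmes that are not tailored and do not involve the community, and says that involving families reduces it; this trial is built on that premise. A reader might take the 85% in protocol 11.2 as the trial's retention rate, but the text says "of the participants will remain active in the program when child is 2-months of age", which is the point of enrolment. Families who left before then are never among the 30, so the figure says nothing about loss from 2 to 9 months. The range of 12 to 14 per arm is therefore illustrative, and one loss per arm moves the t-test powers by only about three points.

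Third, the SAP states its condition of 15 per group openly, and the two continuous figures reproduce at that number. That is so: the calculation is sound. What is unstated is that 15 analysed per group means no loss at all from the 30 recruited.

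Finally, the prompt in protocol 11.2 asks for completers only where applicable, so leaving them out breaks no rule. It applies naturally here, since the outcome is a measurement seven months after baseline.

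**Conclusion.** The point holds in a limited form. The 75% and 43% are correct for 15 evaluable infants per arm and are best-case values for a trial that recruits exactly that many. Over an assumed 14 to 12 per arm they become 72% to 65% and 40% to 35%. That the stated figures rest on zero loss does not depend on the range chosen; the size of the fall does.

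The binary 42% is a separate mismatch. A reader might infer that it too is inflated by assuming full retention. It is not: the planned Fisher test gives 52% at 15 per arm and still 45% at 14. The SAP figure is below the planned test's power until loss reaches 13 per arm (38%), and above it from there down.

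Nothing here shows that 30 families are too few for the stated aim of estimating effect size. The results rest on two-sided tests at 0.05, equal loss in both arms, and the SAP's own effect sizes and variances.

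**What to change.** Keep 30 families.

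- **SAP section 3:** label the 15-per-arm powers as best case with no loss. Add the same powers over a stated range of evaluable infants, marked as an assumption, for example 12 to 14 per arm (diet 65% to 72%, BMI change 35% to 40%). Recompute the binary figure with the planned two-sided Fisher test (52% at 15 per arm; 30% to 45% at 12 to 14), or name the method that gave 42%.
- **Protocol 11.2:** state the number of infants expected to complete the 9-month measurement.

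The cost is a few lines of wording. The two continuous powers look slightly less favourable once loss is shown. The sample size, procedures and the SAP's conclusion about power stay as they are.
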